4.5.3 Exploratory Analysis

Unconfirmed ORR will be summarized. Duration of stable disease or response will also be summarized for the subset of patients who were responders or achieved stable disease. Duration of stable disease or response is defined as the time from the start of study medication to documented disease progression as determined by the investigator or death, whichever occurs first.

The relationship between efficacy and baseline characteristics may also be explored. Descriptive statistics for efficacy endpoints in important subgroups defined by baseline characteristics may be summarized. The impact of baseline characteristics on efficacy may be also evaluated using Cox model for time to event endpoints and logistic regression model for dichotomous endpoints respectively.

4.6 Safety Analyses

Safety analysis will be performed on safety analysis population (see section 4.2). Safety will be assessed through summaries of adverse events, including protocol defined events of special interest, changes in laboratory test results, changes in vital signs, and exposure to study drug. Additional safety summaries may also be provided for applicable biomarker selected sub-groups.

4.6.1 Exposure of Study Drug

Study drug exposure, including treatment duration, number of cycles, and dose intensity, will be summarized with descriptive statistics.

4.6.2 Adverse Events

Verbatim description of adverse events (AEs) will be mapped to Medical Dictionary for Regulatory Activities (MedDRA) thesaurus terms and graded according to the NCI CTCAE v4.0. AEs will be summarized by NCI CTCAE grade. Multiple occurrences of the same event will be counted once at the maximum severity.

All AE data will be listed by study site, patient number, AE starting and ending study days, and study day of initiation of another non-protocol anti-cancer therapy after the last administration of study drug. SAEs and deaths data will also be listed.

All AEs occurring on the day of or after administration of the first dose of treatment will be summarized by thesaurus term, appropriate thesaurus levels, and NCI CTCAE v4.0 grade. Severe AEs (Grade ≥ 3), infusion related reactions, AEs relation to study drug, and AEs leading to study drug discontinuation or interruption will be summarized.

Serious adverse events (SAEs), AESIs, and adverse events leading to study drug discontinuation or interruption will be summarized separately.

Deaths and causes of death will be summarized.

Protocol Defined AE Reporting Period

After initiation of study drug, all AEs will be reported until 30 days after the last dose of study drug or until initiation of new anti-cancer therapy, whichever occurs first; SAEs and adverse events of special interest will continue to be reported until 90 days after the last dose of study drug or until initiation of new anticancer therapy, whichever occurs first. Any and treatment related SAEs and AESIs will be reported until study completion.

The above AEs reporting rules may be used to select AEs to be summarized if significant among of AEs are reported outside of the protocol defined AE reporting period.

4.6.3 Laboratory Data

Laboratory data collected during study treatment and for 30 days after the last dose of study drug were classified according to NCI CTCAE grade and following analysis will be performed.

- 1) Summary of Laboratory Values over Time, including descriptive statistics for change from baseline.
- 2) Listing and summary of lab values above or below the normal range and above or below the marked laboratory abnormalities.
- 3) Clinically relevant shifts in laboratory parameters defined as shifts from Grade 0, 1, or 2 at baseline to Grade 3 or 4 post baseline.

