- Uncontrolled pleural effusion, pericardial effusion, or ascites requiring recurrent drainage procedures (once monthly or more frequently)
 - Patients with indwelling catheters (e.g., PleurX[®]) are allowed.
- Uncontrolled or symptomatic hypercalcemia (>1.5 mmol/L ionized calcium or calcium >12 mg/dL or corrected serum calcium greater than ULN)
 - Patients who are receiving denosumab prior to enrollment must be willing and eligible to discontinue its use and replace it with a bisphosphonate instead while in the study.
- Malignancies other than NSCLC within 5 years prior to enrollment, with the exception of those with a negligible risk of metastasis or death (e.g., expected

5-year OS >90%) treated with an expected curative outcome (such as adequately treated carcinoma in situ of the cervix, basal- or squamous-cell skin cancer, localized prostate cancer treated surgically with curative intent, or ductal carcinoma in situ treated surgically with curative intent)

- Women who are pregnant, lactating, or intending to become pregnant during the study
 - Women who are not postmenopausal (≥ 12 months of non-therapy-induced amenorrhea) or surgically sterile must have a negative serum pregnancy test result within 14 days prior to initiation of study drug.
- History of severe allergic, anaphylactic, or other hypersensitivity reactions to chimeric or humanized antibodies or fusion proteins
- Known hypersensitivity to biopharmaceuticals produced in Chinese hamster ovary cells or any component of the atezolizumab formulation
- History of autoimmune disease, including but not limited to myasthenia gravis, myositis, autoimmune hepatitis, systemic lupus erythematosus, rheumatoid arthritis, inflammatory bowel disease, vascular thrombosis associated with antiphospholipid syndrome, Wegener's granulomatosis, Sjögren's syndrome, Guillain-Barré syndrome, multiple sclerosis, vasculitis, or glomerulonephritis (see [Appendix 7](#) for a more comprehensive list of autoimmune diseases)
 - Patients with a history of autoimmune-related hypothyroidism on a stable dose of thyroid-replacement hormone may be eligible for this study.
 - Patients with controlled Type 1 diabetes mellitus on a stable insulin regimen are eligible for this study.
 - Patients with eczema, psoriasis, lichen simplex chronicus, or vitiligo with dermatologic manifestations only (e.g., patients with psoriatic arthritis would be excluded) are permitted provided that they meet the following conditions:

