4.5.6 Laboratory, Biomarker, and Other Biological Samples

4.5.6.1 Samples for Safety Laboratory Tests

Samples for the following safety laboratory tests will be sent to the study site's local laboratory for analysis:

- Hematology (CBC, including RBC count, hemoglobin, hematocrit, WBC count with differential [neutrophils, eosinophils, lymphocytes, monocytes, basophils, and other cells], and platelet count)
- Serum chemistries (glucose, BUN or urea, creatinine, sodium, potassium, magnesium, chloride, bicarbonate or total CO₂, calcium, phosphorus, total and direct bilirubin, ALT, AST, alkaline phosphatase, LDH, total protein, and albumin)
- Coagulation (aPTT or INR)
- For all women of childbearing potential (including those who have had a tubal ligation), a serum pregnancy test at screening. Urine pregnancy tests will be

performed at specified subsequent visits (see [Appendix 1](#)). If a urine pregnancy test is positive, it must be confirmed by a serum pregnancy test.

- Urinalysis (specific gravity, pH, glucose, protein, ketones, and blood); dipstick permitted
- Thyroid function testing (thyroid-stimulating hormone, free T3, free T4)
- HBV serology: HBsAg, total HBcAb
 - If a patient has a negative HbsAg test and a positive total HBcAb test at screening, an HBV DNA test should be performed at screening.
- HCV serology: HCV antibody and (if HCV antibody test is positive) HCV RNA
 - If a patient has a positive HCV antibody test at screening, an HCV RNA test must be performed to determine if the patient has an active HCV infection.
- HIV testing
 - All patients will be tested for HIV prior to inclusion in the study; HIV-positive patients will be excluded.
- EGFR testing
 - If EGFR testing is not available as a part of standard-of-care diagnostic workup, contact the Medical Monitor for additional options. (See [Section 4.1.2](#) for exclusion criteria).

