6.5 SAFETY ANALYSES

Safety will be assessed through summaries of adverse events, including protocol-defined events of special interest, changes in laboratory test results, changes in vital signs, and exposure to study.

Verbatim descriptions of adverse events will be mapped to thesaurus terms using MedDRA. Adverse event data will be listed by study site, patient number, and study day. Events occurring on the day of or after administration of the first dose of treatment will be summarized by thesaurus term, appropriate thesaurus levels, and NCI CTCAE v4.0 grade. Serious adverse events, including deaths, will be listed separately and will be summarized. For events of varying severity, the highest grade will be used in summaries.

Relevant laboratory tests and vital sign (heart rate, respiratory rate, blood pressures, and temperature) data will be displayed by time, with Grade 3 and 4 values identified, where appropriate. Additionally, all laboratory data will be summarized by NCI CTCAE v4.0 grade.

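### The SAP's count of clinically relevant laboratory shifts omits worsening from Grade 3 to Grade 4

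*SAP*

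**What the plan says.** SAP section 4.6.3 starts from grading: "Laboratory data collected during study treatment and for 30 days after the last dose of study drug were classified according to NCI CTCAE grade". It then plans three outputs.

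- Item 1: "Summary of Laboratory Values over Time, including descriptive statistics for change from baseline".
- Item 2: "Listing and summary of lab values above or below the normal range and above or below the marked laboratory abnormalities".
- Item 3: "Clinically relevant shifts in laboratory parameters defined as shifts from Grade 0, 1, or 2 at baseline to Grade 3 or 4 post baseline".

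Protocol section 6.5 adds two displays. Laboratory and vital sign "data will be displayed by time, with Grade 3 and 4 values identified, where appropriate", and "Additionally, all laboratory data will be summarized by NCI CTCAE v4.0 grade".

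On what is measured, Protocol section 4.5.6.1 lists "Serum chemistries (glucose, BUN or urea, creatinine, sodium, potassium, magnesium, chloride" and further analytes. On who may enter, Protocol section 4.1.2 states "Patients with controlled Type 1 diabetes mellitus on a stable insulin regimen are eligible for this study".

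**The concern.** A shift table separates abnormality that arises or worsens on treatment from abnormality that was already there. Excluding a patient who starts and stays at Grade 3 serves that purpose. Excluding a patient who starts at Grade 3 and reaches Grade 4 does not, because that patient has worsened and has moved to the more severe of the two grades the table is about. Item 3 shuts out both, because it admits only baseline Grades 0 to 2.

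At stake is the completeness of one descriptive safety table. The gap would be empty if no one could enter at Grade 3, so the entry criteria have to be checked. Glucose is the analyte of most interest. Diabetes mellitus is a named risk of atezolizumab (Protocol section 5.1.1) and an adverse event of special interest (section 5.2.3), and patients with controlled Type 1 diabetes may enroll.

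**Working it through.** The plan attaches no sample size, power or error rate to this table, so there is no stated figure to reproduce. The check has three steps.

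**1. Which transitions does item 3 cover?** Let *b* be the baseline grade and *g* the post-baseline grade. A worsening that ends at Grade 3 or 4 needs *g* = 3 or 4 and *g* > *b*.

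- From *b* = 0: 0→3, 0→4
- From *b* = 1: 1→3, 1→4
- From *b* = 2: 2→3, 2→4
- From *b* = 3: 3→4

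The total is 3 × 2 + 1 = 7. Item 3 requires *b* = 0, 1 or 2, which gives 3 × 2 = 6. The one left out is 3→4, and nothing else in the SAP adds it back.

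**2. Can a patient start at Grade 3?** The numeric entry limits in Protocol section 4.1.1 cover neutrophils, lymphocytes, platelets, hemoglobin, INR or aPTT, AST, ALT, alkaline phosphatase, bilirubin and creatinine clearance. Section 4.1.2 adds an exclusion for high calcium. The chemistry panel in section 4.5.6.1 also includes glucose, sodium, potassium and magnesium, and neither section sets a numeric limit for these. A Grade 3 baseline is therefore possible for them.

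Two provisions in section 4.1.2 make it less likely. One excludes patients whose metabolic dysfunction or laboratory finding suggests a condition that contraindicates the drug, could affect interpretation of the results or puts the patient at high risk. The other admits Type 1 diabetes only if it is controlled and the insulin regimen is stable. The documents do not reproduce the CTCAE laboratory cut-offs, so they cannot show which of the numeric limits also rule out Grade 3.

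**3. Where would a 3→4 change show up?**

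- *SAP item 1:* it contributes to the change-from-baseline statistics, but these do not count patients whose grade worsened.
- *SAP item 2:* the value is listed and summarized as abnormal, without reference to baseline grade.
- *Protocol 6.5:* the value is flagged and summarized as Grade 4. As described, this does not separate a patient who moved from Grade 3 to 4 from one who entered at Grade 4.
- *Adverse event tables (Protocol 5.3.5.5, SAP 4.6.2):* it appears if the change is symptomatic, alters study drug, leads to an intervention or a change in concomitant therapy, or is judged clinically significant. Events are then tabulated at maximum severity.
- *SAP item 3:* it does not appear.

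Item 3 is the only planned laboratory output that sets baseline grade against post-baseline grade, and it is the one that misses this change.

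**The case against.** The strongest reply is that the patient is visible in several other places. None of the other laboratory outputs is restricted by baseline grade. A move from Grade 3 to Grade 4 is also likely to meet at least one of the criteria that make a laboratory change an adverse event. For diabetes there is the further route of special-interest reporting, which SAP section 4.6.2 summarizes separately. This stands, and it limits the point to how one table classifies a change. It does not remove the point: adverse event reporting depends partly on investigator judgement, whereas a grade comparison is systematic.

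A reader might go further than the documents allow in four ways.

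- *That these patients are never counted at all.* They are absent only from the shift count.
- *That shift rates are biased low because patients at Grade 3 at baseline stay in the denominator.* Section 4.6.3 states no denominator for item 3. The table could equally be reported among patients with baseline Grade 0 to 2.
- *That some definite share of the 150 patients is affected.* The documents give no baseline grade frequencies. Any share would be a guess, and it would count patients at risk of being missed, not missed events.
- *That a swing from a severe high value to a severe low value is also lost.* This would follow only if one undirected grade were used per test. Item 3 is silent on direction, so the text does not establish it.

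**Conclusion.** The point holds in a narrow form. The definition covers six of the seven worsening transitions that end at Grade 3 or 4, and the omitted one is Grade 3 to Grade 4. The consequence is that such a change would not be identified as a worsening from baseline in the shift table, although the Grade 4 value itself would be reported elsewhere.

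This conclusion assumes that item 3 is programmed as written. It also relies on the absence of numeric entry limits for some panel tests, which makes a Grade 3 baseline possible though probably uncommon. The number of patients cannot be estimated from the documents. The table is descriptive, and no endpoint, test or error rate depends on it. Importance is low, but the correction is cheap enough to make.

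**What to change.** Reword SAP section 4.6.3, item 3, to: *any worsening in CTCAE grade from baseline to a post-baseline Grade 3 or 4, including Grade 3 to Grade 4.* All seven transitions are then covered, and a patient who stays at Grade 3 is still not counted. Optionally, tabulate the high and low directions separately for tests graded in both, which would also settle a detail the text leaves open.

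The cost is one SAP sentence and a small change to the shift-table program. No new data, visits or patients are needed. Shift counts may come out slightly higher.

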4.6.4 Vital Signs

Vital sign (heart rate, respiratory rate, blood pressures, and temperature) data will be summarized by time and by NCI CTCAE grade, where appropriate.

4.6.5 Medications and Other Treatments

Previous and concurrent medical conditions, previous and concomitant medications, and other anti-cancer treatment will be summarized. .

4.7 Biomarker Analyses

Biomarker analysis will be based on Biomarker analysis population, which is all patients who receive at least one dose of study drug and have evaluable baseline biomarker assessment, as defined in section 4.2.

The blood tumor mutational burden (bTMB) assay is a blood-based, circulating tumor DNA (ctDNA) next generation sequencing (NGS) test that will be used as an aid in the identification of non-small cell lung cancer (NSCLC) patients most likely to respond to atezolizumab, a

programmed death-ligand (PD-L1) blocking antibody. The NGS-based assay counts the total number of somatic mutations (single nucleotide variants (SNVs) excluding driver mutations) over a 1.25 megabase (Mb) region of coding DNA in ctDNA isolated from fresh plasma derived from whole blood. bTMB is reported as a whole integer score.

The bTMB assay has been analytically validated and clinically validated retrospectively (ESMO 2017 Gandara presentation and Fabrizio poster and manuscript in review). The assay detects SNVs down to 0.5% allele frequency across 394 genes from as little as 1% tumor content in a cell free DNA (cfDNA) sample. Tumor content is estimated by determining the maximum somatic allele frequency (MSAF). All samples in the biomarker evaluable population have MSAF $\geq 1\%$. The FDA approved the IDE for the bTMB assay in 2017, and the assay is now being used to prospectively enroll 1L NSCLC patients in the BFAST trial.

4.7.1 Primary Biomarker Analyses

K-M curves and a log-rank test will be used to evaluate the differences in PFS between bTMB high versus low groups at 16 and 10 two different cutoff points (i.e. bTMB ≥ 16 vs < 16 , and bTMB ≥ 10 vs < 10). The Gatekeeping testing procedures will be used to test PFS differences at these two primary bTMB cut off points. PFS difference at cutoff point 16 will be tested first. If there is statistical significance in PFS difference bTMB ≥ 16 vs < 16 groups, we will claim statistical significant difference in PFS between bTMB ≥ 16 vs < 16 groups, and we will further test PFS difference at cutoff 10. We can only claim PFS difference between bTMB ≥ 10 vs < 10 groups if both tests for cutoff point 16 and cut off point 10 are statistically significant.

The statistical tests for primary analysis as well as for other analyses comparing efficacy differences between bTMB high group vs low group will be two-sided at a significance level of 0.10. The corresponding bTMB group differences will be estimated and two-sided 90% confidence interval will be provided. All other statistical tests used in the study will be two-sided at level of 0.05. Their corresponding point estimators will be estimated and two-sided 95% confidence interval will be provided.

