3.1 Protocol Synopsis

The protocol synopsis (see protocol).

3.2 Objectives and Endpoints:

The objectives and corresponding endpoints for the study are outlined in table below.

Objectives	Corresponding Endpoints
Primary Efficacy Objective:	
To evaluate the clinical efficacy of Atezolizumab	ORR according to RECIST v1.1 as assessed by the investigator
Secondary Efficacy Objective:	
To evaluate the efficacy of Atezolizumab	Investigator-assessed PFS according to RECIST v1.1
	Investigator-assessed disease control rate and duration of response according to RECIST v1.1
	Overall survival
Safety Objective:	
To evaluate the safety and tolerability of atezolizumab	Incidence of adverse events, with severity determined through use of NCI CTCAE v4.0
Primary Biomarker Objectives:	
To evaluate whether "positive" bTMB (defined as bTMB ≥ 16 , and bTMB ≥ 10) is associated with improved PFS with the treatment of atezolizumab	Relationship between PFS and bTMB (≥ 16 vs < 16) and between PFS and bTMB (≥ 10 vs < 10)
Secondary Biomarker Objective:	
To evaluate whether "positive bTMB" defined at various bTMB cutoff points or quantiles can predict for improved PFS with atezolizumab.	Relationship between PFS and various bTMB cutoff points, defined as range 4 to 24 by twos, and quantiles, except the primary cutoff points 16 and 10
To evaluate the correlation between clinical outcomes including but not limited to PFS rate at 6, 9, and 12 months, ORR, disease control rate and various definitions of positive bTMB.	Relationship between efficacy endpoints including PFS rate at 6, 9, and 12 months, disease control rate, ORR and various bTMB cutoff points and quantiles

Exploratory Biomarker Objectives in Blood:	
To evaluate whether higher expression of an immune-related gene signature in blood PBMCs predicts for improved PFS with atezolizumab	Relationship between PFS and expression of an immune gene signature in PBMCs
To assess whether bTMB is altered as a result of treatment with immunotherapy	Relationship between bTMB and treatment with immunotherapy
To assess the status of additional circulating biomarkers related to immunotherapy and NSCLC and outcomes with atezolizumab	Relationship between circulating biomarkers related to immunotherapy and NSCLC and efficacy
Exploratory Biomarker Objectives in Tissue:	

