4.7.2 Secondary Biomarker Analyses

K-M curves and a log-rank test will be used to evaluate the differences in PFS between bTMB mutation high versus low groups as measured by an NGS-based mutation burden assay in blood at various cutoff points other than the primary cut off points 16 and 10. These cutoff points are defined as range 4 to 24 by twos and quartiles.

Descriptive statistics for PFS curves including median PFS time and 6-, 9-, and 12-month PFS probabilities will be estimated for various bTMB cutoff points. OS will be analyzed in a similar way as PFS. ORR and DCR will also be summarized by various bTMB cutoff points. The Brookmeyer-Crowley methodology will be used to construct the CI for the median. Greenwood's formula will be used to construct the CI for the landmark PFS.

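### The gate in SAP 4.7.1 covers only PFS; other bTMB comparisons, OS in particular, get a two-sided 0.10 without being gated or labelled descriptive

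*SAP*

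**What the plan says.** **The gate (SAP 4.7.1).** "The Gatekeeping testing procedures will be used to test PFS differences at these two primary bTMB cut off points". The order is fixed: "PFS difference at cutoff point 16 will be tested first", and a difference at 10 may be claimed only if both tests are significant.

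**The level (same section, next paragraph).** Tests for the primary analysis and for "other analyses comparing efficacy differences between bTMB high group vs low group will be two-sided at a significance level of 0.10". The paragraph adds: "The corresponding bTMB group differences will be estimated and two-sided 90% confidence interval will be provided". All remaining tests in the study are set at 0.05.

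**The other endpoints (SAP 4.7.2).** The section opens with K-M curves and a log-rank test for PFS at secondary cutoffs, then says: "OS will be analyzed in a similar way as PFS". For response: "ORR and DCR will also be summarized by various bTMB cutoff points". Median PFS and the 6-, 9- and 12-month PFS probabilities are to be estimated as descriptive statistics.

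**The objectives (SAP 3.2).** One secondary biomarker objective covers "clinical outcomes including but not limited to PFS rate at 6, 9, and 12 months, ORR, disease control rate" against various definitions of positive bTMB. OS is not named in it.

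**The cutoffs.** SAP 4.7.2 introduces the secondary PFS cutoffs as those other than 16 and 10, then defines them as 4 to 24 in steps of two plus quartiles, a range that contains both. In SAP 3.2 the exclusion of 16 and 10 stands in the PFS row only. Protocol 6.6.2 has no exclusion.

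**The concern.** A fixed-sequence gate limits the chance of a false bTMB finding: if PFS at 16 is not significant, testing stops. Here it stops for PFS only. The next paragraph gives the other high-versus-low comparisons their own 0.10, with no condition on the gate. PFS at 16 could therefore fail, OS at the same cutoff could reach p < 0.10, and the report could call the OS difference significant under the SAP's own rule. The protection that the gate gives would then be narrower than a reader of 4.7.1 would suppose. This is multiplicity over endpoints at the two pre-specified cutoffs, separate from the number of secondary cutoffs examined.

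**Working it through.** **1. Is 0.10 the working level?** The power table in SAP 4.1 should follow from two-sided 0.10. Inputs from SAP 4.1: n = 150, median PFS 4 months in the shorter-PFS group, HR 0.6, 12-month accrual, 18-month follow-up after the last patient.

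- Hazards: λ = ln 2 / 4 = 0.1733 and 0.6 × 0.1733 = 0.1040.
- P(event) = 1 − [exp(−18λ) − exp(−30λ)] / (12λ) = 0.9814 and 0.9121.
- With 25% in the shorter-PFS group, D = 150 × (0.25 × 0.9814 + 0.75 × 0.9121) = 139.4 events.
- Power = Φ(√(D·p·(1−p)) × |ln HR| − 1.645) = Φ(√(139.4 × 0.25 × 0.75) × 0.5108 − 1.645) = Φ(0.967) = 83.3%.
- The 50th and 75th percentile splits give 91.9% and 84.5%.

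The SAP states 83%, 92% and 84%. With 5% dropout spread over 30 months the results are 82.9%, 91.7% and 84.2%. The level is consistent between 4.1 and 4.7.1.

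**2. Error of the gate alone.** PFS at 10 is tested only after PFS at 16 succeeds, so P(any false PFS finding) = P(PFS at 16 rejects) = 0.10.

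**3. Gate plus ungated OS.** The two events add up exactly:

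P(gate or OS) = 0.10 + P(OS significant and PFS at 16 not significant).

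If all tests were independent, the gate with OS at one cutoff gives 1 − 0.9² = 0.19, and with OS at both cutoffs 1 − 0.9³ = 0.271. The tests are correlated, so two inputs that the documents lack must be assumed:

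- *Correlation between cutoffs, c.* For nested groups c = √[p16(1 − p10) / (p10(1 − p16))], where p is the share at or above the cutoff. Shares of 25% and 50% for 16 and 10 give √(0.25 × 0.50 / (0.50 × 0.75)) = 0.58; 40% and 60% give 0.67; 20% and 40% give 0.61. Range used: 0.5 to 0.7.
- *Correlation between the PFS and OS statistics, r.* Range used: 0 to 0.9.

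The four z-statistics (PFS and OS, each at 16 and 10) were drawn as multivariate normal with mean zero. PFS at one cutoff and OS at the other have correlation r × c. A result is significant if |z| > 1.645.

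| r | c | Gate or OS at 16/10 | OS significant, PFS at 16 failed | Gate or OS at 16 only | OS at 16 significant, PFS at 16 failed |
|---|---|---|---|---|---|
| 0 | 0.5 | 0.258 | 0.158 | 0.190 | 0.090 |
| 0.5 | 0.5 | 0.244 | 0.144 | 0.175 | 0.075 |
| 0.5 | 0.7 | 0.230 | 0.130 | 0.175 | 0.075 |
| 0.8 | 0.7 | 0.205 | 0.105 | 0.151 | 0.050 |
| 0.9 | 0.7 | 0.191 | 0.091 | 0.137 | 0.036 |

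A patient-level simulation with no bTMB effect (120 evaluable patients, 12-month accrual, 18-month follow-up, assumed PFS and OS models with correlation about 0.46) agrees: about 25% for gate or OS at 16/10, and about 14% for OS significant with the gate failed.

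**4. After the fix.** If the other comparisons carry no significance claim, or if OS follows PFS in the fixed sequence, the first test is again PFS at 16. The chance of any false claim when bTMB has no effect returns to 0.10. The power table in SAP 4.1 does not change.

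**The case against.** The strongest reply is that SAP 4.7.1 only sets a level for whatever tests exist, and that 0.10 is a per-test level, never presented as the error over all endpoints. The word claim is used only for the gated PFS results. OS by bTMB stands under a secondary heading, and Protocol 6.7.2 calls the study hypothesis-generating. All of this is accurate. It does not settle the matter, because the SAP chose formal gatekeeping and still assigned a significance level to the other comparisons without saying what a significant result there would mean. The hypothesis-generating remark is made to justify optional interim analyses.

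A second reply is that OS at 16 and 10 may not be tested at all. If a similar way refers to the method of 4.7.2, its cutoffs are introduced as other than 16 and 10; if it reaches back to 4.7.1, it might carry the gate with it. This stands in part: the documents allow OS tests at 16 and 10 but do not state them. The exclusion is written for PFS, and it would be odd to examine OS at the neighbouring cutoffs but not at the two pre-specified ones.

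Third, with OS at 16 only, the chance of a false OS result given that PFS at 16 has failed is at most 0.090 / 0.90 = 0.10. That is correct; the excess lies in the combined error.

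A reader might go further and infer that ORR, DCR and the landmark PFS rates are also tested at 0.10, which would give a much larger error. The documents do not support this. ORR and DCR are summarised and landmark PFS is estimated, with no test named for any of them.

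**Conclusion.** The concern holds in a limited form, and it is minor. The gate covers PFS only, and a two-sided 0.10 applies to other bTMB efficacy comparisons that are neither gated nor labelled descriptive. OS is the only other endpoint for which a log-rank test follows from the text.

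If OS is tested at 16 and 10, a false significant result on the gate or OS has probability of about 0.19 to 0.26, against 0.10 for the gate alone. OS is significant while PFS at 16 has failed in about 9 to 16% of trials with no bTMB effect. With OS at 16 only, the figures are 0.14 to 0.19 and 4 to 9%. They rest on the assumed correlations (PFS/OS 0 to 0.9, cutoffs 0.5 to 0.7) and on reading OS as tested at the primary cutoffs.

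A reader might infer that the SAP plans to declare a bTMB effect on OS after PFS has failed. It does not say so. It leaves the possibility open, and that is what needs closing.

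**What to change.** In SAP 4.7.1, limit the 0.10 significance rule to the two gated PFS tests. Then add a sentence such as: All other efficacy comparisons by bTMB group, including OS at cutoffs 16 and 10, are descriptive; estimates and 90% confidence intervals are reported, and any p-value is labelled nominal.

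If a formal OS claim is wanted, append it to the existing gate instead: PFS at 16, PFS at 10, OS at 16, OS at 10, each at two-sided 0.10 and each tested only if all earlier tests succeed.

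The cost is one sentence and some table footnotes. No patients, data, estimates or intervals are lost. The downside is that a nominally significant OS difference can no longer be called significant when the PFS gate fails; under the second option this includes failure at cutoff 10.
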